## **II. Specific Aims:**

Primary Aim 1: To determine whether QEEG technology can predict whether a patient with MDD will respond to CBT.

Hypothesis 1: Clinical response (defined as >50% change in HAMD-17 from beginning to endpoint) will correlate with changes in QEEG metrics (ATR, EEG Bispectrum, cordance estimates) from beginning to two weeks after starting treatment.

Primary Aim 2: To determine whether there are unique biological changes in patients undergoing CBT, as measured by the QEEG, that are different than those associated with antidepressants (SSRIs).

Hypothesis 2: QEEG parameters, different from those that predict response to pharmacotherapy, will be associated with response to CBT.

Secondary Aim 1: To determine whether there are correlations between QEEG patterns and changes in clinical functioning, assessed by clinical and self-rated instruments (SF-36, Symptom Questionnaire, Beck Depression Inventory), in both arms (CBT vs. escitalopram).

Secondary Aim 2: To determine whether there are any correlations between QEEG metrics and clinical variables (gender, age, comorbid anxiety, chronicity of depression).

Secondary Aim 3: To determine whether the behavioral processes associated with reward responsiveness in a depressed population change as a function of treatment.

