## V. Study Procedures

### a) *Study visits and parameters to be measured:*

The study involves the enrollment of 30 outpatients with major depressive disorder.

Patients screened for the study and found to be eligible will return for their baseline visit after one week, at which eligible patients (n = 30) will be randomized to either CBT or to standard pharmacotherapy with an SSRI (escitalopram 10-20mg) for 12 weeks.

The CBT group will receive twelve weekly 50-minute individual sessions over the course of 12 weeks conducted by experienced therapists who are trained in manual based CBT. The medication group will receive open label treatment of escitalopram, 10-20 mg/day, flexible dose, for 12 weeks, and will be seen every two weeks by a study physician. In both arms, study assessors, who are blind to treatment condition, will assess patients monthly (week 0, 4, 8, and 12), and are responsible for the primary outcome measure (HAMD-17).

The QEEG will be administered 5 times during the study (week 0, 1, 2, 8 and endpoint) allowing us to assess whether there are any correlations between QEEG patterns and changes in clinical functioning. We will record EEG from a fronto-parieto-temporal derivation using a 4-channel EEG Monitor (Aspect Medical Systems) connected to the subject via disposable EEG electrodes. The adhesive material of the electrodes is similar to that found in ECG electrodes. All recordings will be analyzed off-line to generate QEEG metrics. Once such QEEG metric, the ATR, is a complex index derived from left-right asymmetry of combined theta+alpha (4-12Hz) power, relative theta power, and percent change from baseline in relative theta power, and ranges from 0 (low probability of response) to 100 (high probability of response). De-identified data will be shared with Aspect Medical Systems for offline calculation of EEG-based metrics.

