## VI. Statistical Analysis

- a) *Statistical Plan:* The Mann-Whitney U test will be used to analyze differences in changes of QEEG between responders and non-responders to CBT. We will use logistic regression with the outcome being response/no response on the HAMD-17 and the predictors being other EEG measures. We will test the predictors in a stepwise manner given the limited power with a small N. A power calculation based on a previous QEEG study conducted in our clinic reveals that, to achieve power = 0.80, we would need 34 subjects per group. With N = 30 per group (60 subjects total), our power is 0.76. Power for the current study, with N = 15 per group, is 0.47. While this study is underpowered due to the small N, the goal of this study is to act as a pilot study which can help measure effect sizes, providing a foundation for future, larger projects.

For secondary aims, we will use Pearson r's for pairs of continuous measures, or point-biserial r for pairs of dichotomous and continuous measures.

Data from the Signal Detection Fact Task will be analyzed by [name] at Harvard University. Response bias will be the main variable of interest, whereas reaction time, hit rates, and discriminability values will provide control variables. Analyses of variance (ANOVAs) will be used to investigate variables across the three blocks. Discriminability and response biases will be computed using standard formulae (e.g. McCarthy and Davidson 1981).

- b) *Study Endpoints:* Endpoints will be defined as the final study visit at the end of the 12 weeks, or the termination/final visit for patients who choose to (or have to) end participation in the study prematurely.

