Quantitative Electroencephalogram (QEEG) Predictors of Response to Psychotherapy
Versus Antidepressant Treatment in Depression

Identifiers: NCT00824044

Unique Protocol ID: 2008-P-000838

Date prepared: 12/7/2017

Summary:

A-priori expectation from prior **medication** work is a decrease in theta activity from baseline at week 1 in responders, and an increase in non-responders. Prior work showed an increase in theta activity in **placebo** responders (and little change in non-responders). (See attached manuscript that describes changes in theta Cordance over time in both placebo and medication groups. See Fig 4 on page 128.) Also, ATR is expected to be higher in medication responders than non-responders after 1 week on antidepressant.

Methods:

ATR and Power metrics were calculated from available EEGs at baseline and subsequent visits. Change in Power between baseline and subsequent visits were derived. The data were analyzed for 3 groups: Pooled, Drug-only, Drug+CBT.

In a completer analysis (not an intent to treat), independent sample t tests were used to assess the relationship between responders (greater than or equal to 50 % reduction in the primary outcome (HAMD-17 score)) and change in QEEG metrics across time.

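### Primary Aim 2 compares CBT with escitalopram, but no planned test contains a treatment term and the SAP lists no CBT-only analysis set

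*Protocol*

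**What the plan says.** Protocol section II, Primary Aim 2, looks for "unique biological changes in patients undergoing CBT, as measured by the QEEG, that are different than those associated with antidepressants (SSRIs"). Hypothesis 2 under it reads "QEEG parameters, different from those that predict response to pharmacotherapy, will be associated with response to CBT". Section V a) supplies the comparator: patients "will be randomized to either CBT or to standard pharmacotherapy with an SSRI", and section IV gives the allocation as 1:1.

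The analyses given for the primary aims are:

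- Protocol section VI a): "The Mann-Whitney U test will be used to analyze differences in changes of QEEG between responders and non-responders to CBT".
- Protocol section VI a): "logistic regression with the outcome being response/no response on the HAMD-17 and the predictors being other EEG measures", with predictors entered stepwise.
- SAP, Methods: "The data were analyzed for 3 groups: Pooled, Drug-only, Drug+CBT".
- SAP, Methods: "In a completer analysis (not an intent to treat), independent sample t tests were used to assess the relationship between responders" and change in QEEG metrics over time.

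Section VI a) also lists correlations for the secondary aims and ANOVAs across blocks of the reward task. Neither names treatment as a factor.

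**The concern.** Aim 2 asks whether QEEG change under CBT differs from QEEG change under an SSRI. Hypothesis 2 asks whether the link between QEEG and response differs by treatment. The first needs a between-arm difference and the second needs an interaction. The plan specifies neither, and gives no rule for deciding Hypothesis 2. Pooling the arms in a t test by responder status does not help, because treatment does not enter that test.

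What remains is an informal reading of one arm's p-value against the other's, and the SAP does not clearly provide even that. As labelled, its sets contain no CBT-only set, and Drug+CBT matches neither randomised arm. One of two primary aims therefore cannot be validly answered by following the plan. The protocol says the pilot is meant to measure effect sizes, yet no estimate is specified for this contrast.

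**Working it through.** **1. What each test can show**

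| Test | Patients | Compares | Treatment term |
|---|---|---|---|
| Mann-Whitney (protocol VI) | CBT arm | responders v non-responders | none |
| Logistic regression (protocol VI) | not stated | response on EEG measures | none named |
| t tests (SAP) | Pooled; Drug-only; Drug+CBT | responders v non-responders | none |

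The Drug+CBT label has three possible readings. As both arms together, it duplicates Pooled. As combined treatment, it describes an arm that was not randomised. As a mislabelled CBT arm, it would give a within-CBT result but still no between-arm test.

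**2. The protocol's own power figures**

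Section VI gives 34 per group for power 0.80, 0.76 at 30 per group and 0.47 at 15 per group. It gives no effect size, alpha or sidedness. I assume two-sided 0.05. With the normal approximation, power = Φ(d/√(2/n) − 1.96). At d = 0.688 this gives 0.81 at n = 34 (the smallest n reaching 0.80), 0.76 at 30 and 0.47 at 15, so the three figures agree with each other. The noncentral t at 34 per group and power 0.80 gives d = 0.69 (and 0.446 at 15 per group). These are two-group figures and do not cover an interaction. The steps below use d = 0.69 and the noncentral t.

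**3. Side-by-side p-values**

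Assume 15 per arm, split 8 responders and 7 non-responders, and one metric. Within-arm power is p = 0.235.

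- Same true effect in both arms, significant in CBT but not in drug: p(1 − p) = 0.235 × 0.765 = 0.18.
- Same true effect, exactly one arm significant: 2p(1 − p) = 0.36 (0.39 with the normal approximation).
- Effect in CBT only, significant in CBT but not in drug: 0.235 × 0.95 = 0.22.

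Under equal effects an interaction test would reject 0.05 of the time.

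Sensitivity of the CBT-only split under equal effects:

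| d | Split per arm | p | p(1 − p) |
|---|---|---|---|
| 0.3 | 8/7 | 0.084 | 0.08 |
| 0.69 | 8/7 | 0.235 | 0.18 |
| 1.2 | 8/7 | 0.574 | 0.24 |
| 0.69 | 5/5 | 0.161 | 0.14 |
| 0.69 | 12/3 | 0.168 | 0.14 |

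**4. The pooled t test**

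By simulation at 8/7 per arm, it rejects about 0.14 of the time if the effect is in one arm only, and 0.03 if the effects are equal and opposite, because they cancel. The reversal is an illustration only: the opposite theta direction mentioned in the SAP concerns placebo responders, not CBT.

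**5. What the missing contrast would deliver**

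Interaction SE in SD units = √(Σ 1/n over the four cells). For cells 8, 7, 8, 7: √(2/8 + 2/7) = 0.732, df = 26, t = 2.056, half-width 2.056 × 0.732 = 1.50.

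| Cells | Half-width of 95% CI (SD) | Power, interaction 0.69 | Power, interaction 1.38 |
|---|---|---|---|
| 8, 7, 8, 7 | 1.50 | 0.15 | 0.44 |
| 6 each (24 completers, assumed) | 1.70 | 0.13 | 0.36 |
| 5 each (20 completers, assumed) | 1.90 | 0.11 | 0.31 |
| 12, 3, 12, 3 | 1.88 | 0.11 | 0.31 |

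The between-arm difference in QEEG change has a half-width of 0.75 SD with 15 per arm and 0.94 SD with 10 per arm.

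**The case against.** - **Comparison with earlier drug work.** The SAP opens with the pattern expected from prior medication studies, and the protocol's only arm-specific test is in CBT, so Hypothesis 2 might mean CBT against a known drug pattern. But neither document states such a rule. Aim 2's wording, the randomised SSRI arm and protocol section VIII b), which speaks of comparing CBT responders with SSRI responders, favour a within-study contrast.
- **More than one estimand.** Section VIII b) refers to baseline markers, not change. This is a fair caution, but it is a benefits statement, whereas Aim 2 speaks of changes.
- **Form of the model.** ATR already contains a change from baseline, and response could be the outcome instead. Hypothesis 1 itself speaks of change in ATR. A logistic model with an EEG-by-treatment term is an alternative parameterisation. Either would do, and the plan has neither.
- **The CBT-only gap is in the SAP only.** This stands: the protocol has a CBT-only test. That test serves Aim 1 and has no escitalopram comparator.
- **It is an admitted pilot, and the interaction would rarely be conclusive.** This is true. It argues for an estimate with a confidence interval, not for comparing p-values.
- **Larger effects separate better.** At d = 1.2 the CBT-only pattern occurs with probability 0.55 if the effect is in CBT only (0.574 × 0.95), against 0.24 under equal effects. An equal effect still gives the misleading split about a quarter of the time.

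**Conclusion.** The concern holds and must be fixed. Neither document specifies an analysis that answers Primary Aim 2 or Hypothesis 2, and the SAP's set labels leave it unclear whether a CBT-only result exists at all. Reading separate tests side by side would produce the CBT-only pattern with probability 0.18 when the arms do not differ and 0.22 when the effect is in CBT only.

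The omission is established from the text and needs no assumption. The probabilities rest on d = 0.69, two-sided 0.05, an assumed 8/7 split and a single metric. Other effect sizes, fewer completers and an unbalanced split move the equal-effects figure between 0.08 and 0.24, without making side-by-side p-values a valid test of a difference.

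**What to change.** 1. Name the QEEG metrics and one time point. Hypothesis 1 uses two weeks; the SAP's expectation is for week 1.
2. For each metric fit one model to all analysed patients from both randomised arms: QEEG change = treatment + response + treatment × response. Report the interaction with its 95% CI as the Hypothesis 2 result.
3. Report the between-arm difference in QEEG change with its 95% CI for Aim 2 as worded.
4. Name one lead metric, or state how many interaction tests there are and adjust. Three unadjusted independent tests give 1 − 0.95³ = 0.14.
5. Treat within-arm tests as descriptive, add a treatment term to the pooled analysis, and state that significance in one arm only is not evidence of a difference.
6. Reconcile the SAP's set labels with the randomised arms. If a comparison with earlier drug studies was intended, say so and give the rule.

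The cost is one extra model per metric on data already collected, plus SAP wording. The SAP is dated 12/7/2017 and written in the past tense, so if the data had already been analysed the model must be labelled post hoc. The price is low precision, as shown in the working: the result is an effect-size estimate, which suits a pilot.

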### **III. Subject Selection**

#### *A. Inclusion/exclusion criteria:*

##### Inclusion Criteria:

1. Subjects will be adults, ages 18 to 75 years.
2. Written informed consent
3. MDD, current according to the fourth version of the Diagnostic and Statistical Manual for Mental Disorders (DSM-IV)
4. 17-item Hamilton Depression Rating Scale (HAM-D-17) score of  $\geq 14$  at screen.
5. Subjects who are not currently taking any antidepressant or other psychotropic medications and who have been free of these medications for 4 weeks prior to screening visit.

##### Exclusion Criteria:

1. Women who are pregnant, lactating, or planning a pregnancy during the study.
2. Women of child bearing potential who are not using a medically accepted means of contraception (to include oral contraceptive or implant, condom, diaphragm, spermicide, intrauterine device, tubal ligation, or a partner with vasectomy).
3. Any uncontrolled psychiatric disorder.
4. Current use of psychotropic medications: including lithium, benzodiazepine sedatives (such as diazepam, lorazepam, alprazolam, or clonazepam), other sedatives (such as buspirone, zolpidem, and zaleplon), anti-seizure medications (such as valproic acid, or carbamazepine),
5. Current use of other exclusionary medications: beta-blockers (such as metoprolol or propranolol), dehydroepiandrosterone (DHEA), entacapone, hydroxytryptophan (5-HTP), ginkgo, St. John's wort (hypericum), and warfarin (Coumadin).

6. Psychotic features in the current episode or a history of psychotic features.
7. Alcohol or substance abuse or dependence within the past three months.
8. History of head trauma or seizure disorder.
9. History of intolerance of the study medication.
10. Failure to respond to escitalopram up to 20 mg for at least 6 weeks.
11. Failure to respond to 2 or more adequate antidepressant trials (6 weeks or longer on a therapeutic dose, equivalent to fluoxetine 40mg) in the current episode.
12. Currently enrolled in other depression-focused psychotherapy and unwilling to cease treatment.
13. Subjects who, per clinical judgment, are not appropriate candidates for CBT or SSRIs.
14. History or current diagnosis of the following DSM-IV psychiatric illness: organic mental disorder, schizophrenia, schizoaffective disorder, delusional disorder, psychotic disorders not otherwise specified, bipolar disorder, patients with mood congruent or mood incongruent psychotic features, patients with substance dependence disorders, including alcohol, active within the last 3 months.
15. Serious suicide or homicide risk, as assessed by the evaluating clinician or a score of 4 on the third item of the HAM-D.
16. Serious or unstable medical illness, including cardiovascular, hepatic, renal, respiratory, endocrine, neurologic or hematologic disease

*B. Source of Subjects and Recruitment Methods:*

Patients will be recruited per usual methods, including IRB-approved advertising in newspapers, television and radio, and referrals from other clinicians.

Patients of all ethnic and racial categories will be included.

Children and adolescents under age 18 will not be included. Children under age 18 will not be included. There are limited data available about the efficacy and safety of escitalopram as an antidepressant in children; it would therefore be preferable to obtain more adult data prior to testing this treatment in children. Also, the investigators of the Depression Clinical and Research Program have limited experience in pediatric work, and are not board-certified in the treatment of pediatric populations. We also are not trained in the use of the diagnostic instruments necessary for the appropriate assessment of younger children with depression, which differ from those instruments used in adults and older adolescents. As there are many registered antidepressants available for use in depressed children, exclusion of young children from this study should not prevent them from obtaining appropriate, effective treatment with proven agents.

#### **IV. Subject Enrollment**

*A. Methods of enrollment/registration/randomization:*

Patients are usually screened by telephone to determine tentative eligibility for studies. The subjects then are invited to come to MGH for a full psychiatric diagnostic interview. Patients accepted into the study will be registered through the Depression Clinical and Research Program. Randomization numbers will be provided by the study Biostatistician and will be maintained by the research pharmacists at MGH Research Pharmacy, who will administer the open label escitalopram, 10-20 mg/day, to those subjects who have been randomized to receive medication. The randomization will be 1:1, i.e. half of the patients will be randomized to receive escitalopram (10-20 mg/day, flexible dose) and half will be randomized to receive twelve weekly 50-minute

Cognitive Behavioral Therapy sessions. Both treatment interventions have been strongly validated by the literature, and are considered standard of care for this population.

## V. Study Procedures

### a) *Study visits and parameters to be measured:*

The study involves the enrollment of 30 outpatients with major depressive disorder.

Patients screened for the study and found to be eligible will return for their baseline visit after one week, at which eligible patients (n = 30) will be randomized to either CBT or to standard pharmacotherapy with an SSRI (escitalopram 10-20mg) for 12 weeks.

The CBT group will receive twelve weekly 50-minute individual sessions over the course of 12 weeks conducted by experienced therapists who are trained in manual based CBT. The medication group will receive open label treatment of escitalopram, 10-20 mg/day, flexible dose, for 12 weeks, and will be seen every two weeks by a study physician. In both arms, study assessors, who are blind to treatment condition, will assess patients monthly (week 0, 4, 8, and 12), and are responsible for the primary outcome measure (HAMD-17).

The QEEG will be administered 5 times during the study (week 0, 1, 2, 8 and endpoint) allowing us to assess whether there are any correlations between QEEG patterns and changes in clinical functioning. We will record EEG from a fronto-parieto-temporal derivation using a 4-channel EEG Monitor (Aspect Medical Systems) connected to the subject via disposable EEG electrodes. The adhesive material of the electrodes is similar to that found in ECG electrodes. All recordings will be analyzed off-line to generate QEEG metrics. Once such QEEG metric, the ATR, is a complex index derived from left-right asymmetry of combined theta+alpha (4-12Hz) power, relative theta power, and percent change from baseline in relative theta power, and ranges from 0 (low probability of response) to 100 (high probability of response). De-identified data will be shared with Aspect Medical Systems for offline calculation of EEG-based metrics.

The Signal Detection Task will be administered at baseline and at endpoint. In the specific Signal Detection Task we will use, called the Face Game (assessing reward sensitivity), we will present simple cartoon faces (diameter: 25 mm; eyes: 7 mm) in the center of the monitor and at the beginning of the trial. The face has no mouth. After a given delay, either a straight mouth of 11.5 mm (“short mouth”) or 13 mm (“long mouth”) will be presented for 100 ms. Subjects will be instructed to press an appropriate button to decide whether a long or short mouth had been presented. For the present study, the experiment will consist of 300 trials, divided into 3 blocks of 100. Long and short mouths will be presented equally often. A trial will begin with the presentation of an asterisk for 500 ms that will serve as fixation point and warning stimulus that a trial will start. After 500 ms, a mouth-less face will be presented and will stay on the screen until a response is made; after an inter-stimulus interval of 500 ms, one of the two mouths will be presented for 100 ms. Critically, not all correct responses will receive feedback (only positive feedback will be provided). For each block, 40 correct trials will be followed by a reward feedback (“Correct!! You won 5 cents”), presented for 1750 ms immediately after the correct response. For half of the subjects, correct identification of the little mouth will be associated with three times more positive feedback (30/40) than correct identification of the big mouth (10/40). For the other half of the subjects, the contingencies will be reversed. After feedback, an inter-trial interval (ITI) of 250 ms will follow. Subjects will be instructed that the aim of the study is to win as much money as possible, and that they will receive the amount of money won at the end of

experiment (actual money will be shown to the subjects for increasing the credibility of the experiment).

Scales:

Once the patient has agreed to participate in the study by signing the informed consent, the following instruments will be administered by a study assessor who is blind to treatment condition at screen, baseline, and visits 4, 8 and 12:

- a. Structured Clinical Interview for DSM-IV (Spitzer et al, 1989). The SCID-I/P, administered by the clinician, proceeds by modules to the different Axis I disorders. Question here are asked exactly as written, and each is based on the individual criteria from DSM-IV. These scales will rely on retrospective reporting from the participant (screen visit only)
- b. 28-item Hamilton Rating Scale for Depression (HAM-D 28-item) (Hamilton, 1960; 1967; Williams 1988): This version allows scoring of the HAM-D-17, 21-, 25, and 28-item scales. This instrument is completed by the clinician based on his/her assessment of the patient's depressive symptoms, using a structured interview and defined anchor points. The HAM-D aims to quantify the degree of depression in patients who already have a diagnosis of major depression. These scales will rely on retrospective reporting from the participant.
- c. BDI (Beck & Steer, 1987): The Beck Depression Inventory is a widely used 21-item self-report measure that assesses the severity of affective, cognitive, and vegetative symptoms of depression experienced by patients over the past week.
- d. CGI-S and I (Guy, 1976): This measure, based on history and scores on other instruments: a) CGI-S (severity): the current condition of the patient on a scale of 1-7 (1 being normal, and 7 being among the most severely ill patients); b) CGI-I (improvement): the degree of improvement, as perceived by the clinician, since the start of treatment on a scale of 1-7.
- e. Kellner's Symptoms Questionnaire (SQ) (Kellner, 1987). This instrument is completed by the patient based on his/her assessment of the severity of anxiety, depression, somatic symptoms, and hostility.
- f. Quality of Life Enjoyment and Satisfaction Questionnaire (Q-LES) (Endicott, Nee, Harrison, Blumenthal, 1993). This self-report measure is a 16 item sensitive measure of the degree of enjoyment and satisfaction experienced by subjects in various areas of daily functioning. The summary scores have been found to be reliable and valid measures of these dimensions in a group of depressed outpatients.
- g. DAS (Weissman & Beck, 1978): The Dysfunctional Attitude Scale is a 40 item self-report questionnaire that is designed to measure the presence of depressotypic underlying assumptions, or dysfunctional beliefs. It is the most widely used instrument for this purpose.
- h. ATQ-R (Kendall, Howard, & Hays, 1989): The Automatic Thoughts Questionnaire-Revised is a self-rated instrument to assess cognitive self-statements related to

depression. It includes 30 negative self-statements and 10 self-statements reflecting positive affect.

- i. PSS (Cohen et al., 1983): The Perceived Stress Scale is a self-rated instrument to evaluate a patient's level of perceived stress. Patients are asked to endorse to what degree, over the last month, they felt stressed. Each of the 14 statements presented describes a stressful state.
- j. SF36 (Ware, 1993): Medical Outcomes Study (MOS) 36 Item Short-Form Health Survey is a clinician-administered instrument to assess quality of life. It has 36 items and contains subscales that measure physical functioning, physical role functioning, social functioning, emotional role function, general health, energy, mental health, and bodily pain over the past four weeks.
- k. Snaith-Hamilton Pleasure Scale (SHAPS) (Snaith et al., 1995). This short 14-item self rated scale assesses self-reported anhedonia.

Adverse events and changes in concomitant medications will be assessed at each visit with the clinician for subjects randomized to the medication arm. The clinician will inquire about any changes in dosages of medications as well as days the medications were not taken. The importance of taking medications as prescribed and refraining from taking a « holiday » from medication on weekends or at any other time during the study will be emphasized from the time the patient enrolls in the study.

For subjects randomized to psychotherapy, adverse events will be assessed by the CBT therapist at baseline and weeks 2, 4, 6, 8, 10 and 12.

